11. STATISTICAL CONSIDERATIONS AND ANALYTIC PLAN

11.1 SAMPLE SIZE

The sample size of the study is computed on the basis of expectations for the the difference of the pain NRS means between the two arms at final analysis. Based on previous studies (Yildrim 2004 and Harmon 1990), we may expect a difference of the pain NRS means of 2 or more between the two arms, with a standard deviation of the pain NRS of 2 in both arms. For a statistical power of 80%, an alpha error of 5% and a two-sided test, 17 evaluable patients are needed in each group to reach statistical significance (calculation performed with Stata/MP 14.1).

Assuming a potential drop out rate of 10% in each arm, a total of 19 patients need to be randomized to each arm. The total number of patients for the study is 38.

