4.1.2. Alternatives to standard of care

Audio-analgesia, aromatherapy, biofeedback, acupressure, TENS (Transcutaneous Electric Neurologic Stimulation) and massage are popular methods but are not proven to have a significant effect on labor pain. These are not available in our institution. On the other hand hydrotherapy, acupuncture and hypnosis have a proven significance as a tool for pain management during labor.^{xiii} More specifically hypnosis may reduce the overall use of analgesia during labor.^{xiv}

4.1.3. *Hypothesis*

Our primary goal is to evaluate the analgesic benefits of Virtual Reality Hypnosis (VRH) compared to the standard of care (ST) solely.

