5. STUDY OBJECTIVES

5.1 PRIMARY OUTCOME

The primary endpoint is to compare the differences in NRS pain measured before and after the intervention during labor. (T3 minus T1) The Pain Numerical rating Scale (NRS) is a scale from 0 to 10 well known by the medical staff.^{xv xvi}

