10. SELECTION AND WITHDRAWAL OF SUBJECTS

During the prenatal visit (PNV = T0; some weeks before the due date) the pregnant women receive information about the the study and the use of VRH from the midwife. Each patient will be asked for participation in the study, after verifying the presence of the inclusion criteria and absence of any exclusion criteria. The registration checklist is filled in (questionnaire 1). If patients refuse, their motivation will be noted on the refusal questionnaire(questionnaire 4). All the included patients receive sufficient information and time to decide if they want to participate or not. After signing the informed consent (Questionnaire 2 resp) they will be immediately randomized using block randomization (with excel). This will assign the pregnant woman to either control group or the VRH group.

On the day of delivery every included patient will receive standard of care. When the women selected in the VR group are in active labor (NRS pain ≥ 4 , cervical dilatation ≥ 4 cm and regular contractions (every five minutes) we present the VRH treatment (T1).

Patients who refuse the VRH treatment (T1) or remove the VRH headset during(T2) will be asked to fill in questionnaire 4 (refusal questionnaire). They will be considered as drop outs.

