11.4 ANALYSIS

First descriptive analysis will be performed. Qualitative data will be described by frequency and percentage. Quantitative data will be described by mean, standard deviation, median, minimum, and maximum numbers.

Regarding the primary outcome, NRS pain score before and after the intervention will be compared using paired t-test or Mann-Whitney test, depending of data distribution. 95% confidence intervals will be provided.

Regarding secondary outcomes, chi-squared tests will be used to compare frequencies and rates between groups. In case of small cell sizes, we will alternatively use the Fisher's exact test. T-Test or Mann-Whitney test will be used to determine if there is a significant difference between means of the two groups. T-Test or Mann-Whitney test will be also used for all continuous data normally distributed or not such as NRS, Likert scale and physiologic data. Repeated measurements such as Anxiety and Nausea will be handled with appropriate techniques such as paired tests.

Safety variables include the incidence of Serious Adverse Events (SAEs), discomfort and the quality of immediate and distant labor pain analgesia. These data will be tabulated by treatment groups and overall, in contingency table for percentages or in descriptive univariate analyzes for continuous variables.

The Intent-to-Treat (ITT) population will be used for all efficacy and safety analyzes unless otherwise specified. This ITT analysis will include all randomized patients, according to their allocation group.

The Per-Protocol (PP) population will be used to validate the effectiveness of the studied intervention, as specified by the primary outcome. This PP analysis will include all patients in the ITT population who do not have a major violation of the protocol. The list of major violations includes at least:

- Non-administered medication
- Failure to meet an inclusion or exclusion criterion

Patients identified as having major violations will be screened to determine their final exclusion from the PP population, prior to the freezing of the database.

12.QUALITY CONTROL AND QUALITY ASSURANCE

Increased adherence to the protocol is acquired by multiple information sessions about the study for the midwives. Furthermore, a reminder poster will be displayed in their office. Adherence to the protocol by the participants will be monitored daily by a non-blinded investigator (LP) by looking at the daily reports of the study.

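### The paired t-test named for the primary outcome in 11.4 is not the between-arm comparison that 11.1 powers, and 11.1 does not say which score its SD of 2 describes

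*Combined protocol and SAP*

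**What the plan says.** The hypothesis in section 4.1.3 is comparative: "Our primary goal is to evaluate the analgesic benefits of Virtual Reality Hypnosis (VRH) compared to the standard of care (ST) solely". Section 5.1 sets the primary endpoint as a change score; the aim is to "compare the differences in NRS pain measured before and after the intervention during labor. (T3 minus T1").

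Section 11.1 bases the sample size on the "difference of the pain NRS means between the two arms at final analysis". It expects a difference of 2 or more "with a standard deviation of the pain NRS of 2 in both arms. For a statistical power of 80%, an alpha error of 5" per cent, two-sided. This gives 17 evaluable women per arm, raised to 19 for 10% drop-out, 38 in total. The SD is attributed only to the pain NRS. No SD of T3 minus T1 and no T1–T3 correlation appears anywhere.

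For the primary outcome, section 11.4 says: "NRS pain score before and after the intervention will be compared using paired t-test or Mann-Whitney test, depending of data distribution". Two-group wording comes in the next paragraph, which opens with the secondary outcomes: "T-Test or Mann-Whitney test will be used to determine if there is a significant difference between means of the two groups". On the analysis set: "This ITT analysis will include all randomized patients, according to their allocation group".

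**The concern.** There are two gaps between the question, the sample size and the test.

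1. **The test.** A paired t-test asks whether pain changed within women. It gives no estimate of VRH against standard care. Any change common to both arms, such as labor advancing between T1 and T3, counts towards the result, so a significant p-value need not mean that VRH differs from control. The stated alternative, Mann-Whitney, is an independent-groups test and not the rank counterpart of a paired t-test. Letting the data distribution choose between them would change the question as well as the method.

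2. **The SD.** The endpoint is T3 minus T1, but the SD of 2 is not tied to that change or to a single score. If it is the SD of the change, the stated power stands for an unadjusted between-arm comparison of change. If it is the SD of a single score, that power depends on the T1 SD and the T1–T3 correlation, and the plan gives neither.

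**Working it through.** **Inputs from section 11.1:** difference 2, SD 2, two-sided 5%, 80% power, 17 evaluable per arm, 10% drop-out. **Assumptions, not in the documents:** T1–T3 correlation ρ from 0 to 0.7; T1 SD s₁ from 1 to 2; a common shift of 0.5 or 1 point in the paired-test check.

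**Step 1: reproduce the plan's figure.** For a two-sample t-test the noncentrality is 2 / (2·√(2/n)).
- n = 16: 2.83 on 30 df, power 78.1%.
- n = 17: 2.92 on 32 df, power 80.7%.
- Drop-out: 17 / 0.9 = 18.9, so 19 per arm and 38 in total.

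The arithmetic is right, and it is that of a between-arm comparison.

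**Step 2: the paired t-test when VRH has no effect.** Take 17 VRH women, SD 2 at both times and the same mean shift in both arms. The change SD is 2·√(2(1−ρ)), and the noncentrality is shift·√17 / change SD on 16 df. At ρ = 0.5 the change SD is 2, so a 1-point shift gives 1 × 4.123 / 2 = 2.06 and 49% significant.

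| ρ | 0 | 0.3 | 0.5 | 0.6 | 0.7 |
|---|---|---|---|---|---|
| 1-point shift, % significant | 28 | 37 | 49 | 58 | 71 |
| 0.5-point shift, % significant | 11 | 13 | 16 | 19 | 24 |

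**Step 3: power if SD 2 is for a single score.** Set the T3 SD at 2, with 17 per arm and a true difference of 2.
- Unadjusted change: change SD = √(s₁² + 4 − 4ρs₁), 32 df.
- T3 adjusted for T1 (ANCOVA): residual SD = 2·√(1−ρ²), 31 df, averaged over chance T1 imbalance. This does not depend on s₁.

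| Power, % | ρ = 0 | 0.3 | 0.5 | 0.6 | 0.7 |
|---|---|---|---|---|---|
| Change, s₁ = 2 | 52 | 67 | 81 | 88 | 95 |
| Change, s₁ = 1.5 | 62 | 76 | 88 | 93 | 98 |
| Change, s₁ = 1 | 72 | 83 | 90 | 94 | 97 |
| ANCOVA, any s₁ | 79 | 83 | 89 | 93 | 97 |

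The smaller T1 SDs are included because section 10 sets a pain threshold at T1: "When the women selected in the VR group are in active labor (NRS pain ≥ 4". That wording covers the VRH arm; whether controls must also meet it is not spelled out. Over a grid of 75 combinations (s₁ from 1 to 2 by 0.25, ρ from 0 to 0.7 by 0.05), the change score leads in 14, by at most 1.0 point. ANCOVA leads by up to 28 points, mostly at low ρ.

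**Step 4: power if SD 2 is for the change.** The unadjusted change then has 80.7%. With equal SDs at T1 and T3, the ANCOVA residual SD is 2·√((1+ρ)/2), and power is 97.5/93.1/89.4/87.4/85.4% at ρ = 0/0.3/0.5/0.6/0.7.

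**Step 5: floor of the adjusted model.** Its residual SD cannot exceed the T3 SD or the change SD. It is therefore at most 2 under either reading, and power is at least 79.4% with 17 per arm. If all 38 women are analysed the floor is about 84%.

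**Step 6: simulation.** With continuous scores and SD 2 at both times, ANCOVA gave 79.6/83.2/89.4/93.4/97.3% and Mann-Whitney on the change 49.8/63.8/78.0/86.6/94.2% over the same ρ. With whole-number scores confined to the scale (T1 4–10, T3 0–10, assumed means 7), ANCOVA gave 78.1/81.8/87.8/91.8/96.1%. Its type I error stayed at 4.9–5.1%, also with means near the ceiling.

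**The case against.** **Loose wording.** Sections 4.1.3, 5.1 and 11.1 all point to a between-arm comparison, and 11.4 extends its two-group tests to NRS data. So a two-sample test of T3 minus T1 may be what was meant. That is a fair reading of intent, but the extension sits under the secondary outcomes, and the sentence on the primary outcome names a paired test. A pre-specified analysis should not have to be inferred.

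**ANCOVA is partly a preference.** This is true. A two-sample comparison of T3 minus T1 would be valid, and it is the smaller correction. The 28-point advantage occurs only at T1 SD 2 and ρ = 0; at ρ = 0.5 it is 9 points or less, and slightly negative at T1 SD 1. The argument for adjustment is that its floor holds without knowing ρ, the T1 SD or the meaning of the SD of 2.

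**The floor is conditional.** It assumes the plan's own inputs. Power at ρ = 0 is about 77% with 16 evaluable per arm, 74% with 15, and 60% if the T3 SD were 2.5. Cutting scores off at the scale limits gives 78.1%. These cases depart from the plan's inputs and would lower the power of the other tests too.

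**Measurement details.** Section 9 ties T1 and T3 to the AQUA session, and the plan does not say when a control's T3 is taken. Section 10 counts women who refuse or remove the headset as drop-outs, while 11.4 promises an analysis of all randomised women. Both points stand and need a line of text, but neither makes the paired test right.

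**The paired-test rates** assume a test in VRH women alone and a chosen shift. Both are assumptions and illustrate size only. That the test cannot separate a shared change from a VRH effect does not depend on them.

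**Conclusion.** The concern holds. The paired t-test in 11.4 does not test the hypothesis in 4.1.3 and is not what 11.1 powers. With no VRH effect and a common 1-point shift it would be significant in 28% to 71% of trials (17 VRH women, SD 2 at both times, ρ 0 to 0.7).

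The unspecified SD means that the stated 80% cannot be linked to T3 minus T1. The unadjusted change has 80.7% power if the SD is for the change, and 52% to 95% if it is for a single score at both times with ρ from 0 to 0.7. A between-arm model of T3 adjusted for T1 has about 79% or more under either reading. This takes 17 evaluable per arm, a true difference of 2, and an SD of 2 for either T3 or the change. The sample size arithmetic is correct, and nothing here shows that 38 is too few.

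**What to change.** **Section 11.4.** Replace the sentence on the primary outcome with: *NRS pain at T3 is compared between arms by a linear model with arm and NRS pain at T1 as covariate (ANCOVA), in all randomised women as allocated; the adjusted difference is given with its 95% CI. T3 minus T1 is summarised by arm. As a sensitivity analysis for non-normal data, T3 minus T1 is compared between arms by the Mann-Whitney test.* Add how women with no T1 or T3 value are counted, since the model needs both. Reconcile this with the drop-out wording in section 10, and state when T1 and T3 are recorded in controls.

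**Section 11.1.** Check the sources used and state which score the SD of 2 describes.
- If a single score: assuming SD 2 at T1 and T3 and a difference of 2, 17 evaluable women per arm give about 79/83/89/93/97% power for this model at a T1–T3 correlation of 0/0.3/0.5/0.6/0.7.
- If the change: 80.7% for the unadjusted change, and at least about 79% for this model.

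**Cost.** Wording and one model term. Section 9 already schedules both pain scores, so there are no new assessments and n stays 38. The model uses one degree of freedom, its stated power may start just under 80%, and the change score can be ahead by about 1 point in some cases. Women without T1 or T3 are not recovered. T1 is recorded after allocation is known, so it must be taken in the same way in both arms; T3 minus T1 depends on this too.

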11.2 SEQUENCE GENERATION

We created a block randomization in excel. This block randomization, has variable block sizes to decrease the chance of deducing the following allocation. The patients will be randomly allocated in either the either the control group or the VRH group in a 1:1 allocation.

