4. RATIONALE

4.1. CONTEXT AND JUSTIFICATION OF THE STUDY

Labor pain is feared by many women. However some women recall positive feelings about their coping ability with this intense pain. The way they dealt with pain seems more important than the severity of the labor pain. The feeling of being in control, respected and nurtured by caregivers and loved ones is what these women recall mostly.ⁱ

On the other hand, many women recall feelings of suffering, loneliness and helplessness. These negative feelings make the whole childbirth experience unpleasant. Even a posttraumatic stress disorder can develop after childbirth. The ability to cope with this pain is influenced by experiences that took place before childbirth. It is probably more likely to have dysfunctional coping skills when earlier traumas were never resolved.^j We believe that Virtual Reality Hypnosis (VRH) can improve the way women cope with pain during labor. Through self-hypnosis, the focus is moved from pain to positive feelings, thereby women feel less tensed and have a greater sense of self-control.

Secondly women are increasingly striving for a more natural birth, minimizing medical interventions such as cervical examination, pharmacological analgesia, etc. As such they are looking for nonpharmacological approaches to decrease labor pain.

There are different nonpharmacological (see section 4.1.2 alternatives for standard of care) techniques that can reduce side-effects, increase rates of breast feeding, and eventually increase satisfaction.^{ii,iii}

Immersive virtual reality (VR) has been shown to decrease pain in a non-pharmacological way and in a number of different situations.^{iv,v} Studies are positive about the use of immersive VR therapy as analgesia during experimental pain in healthy subjects, changing dressings of burn patients and as an analgesic adjunct during physiotherapy.^{vi vii viii}

The pain accompanied with childbirth is nor acute nor chronic and thereby a complex unique experience for every woman. Some studies suggest that VR can help controlling the pain during the active stage of labor. Outcomes like anxiety, use of pharmacological analgesia and satisfaction have also been studied.^{ix,x,xi}

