14. DATA HANDLING AND RECORD KEEPING

14.1 DATA COLLECTION METHODS AND RETENTION

There are four paper forms per patient that are used to collect the data that we put together in one plastic sheet (folder). Questionnaire 1 is the registration checklist where inclusion and exclusion criteria are checked, the study number and randomization group is noted. Questionnaire 2 is the informed consent signed by the patient and the investigator. Questionnaire 3 is the data collection form used by the investigators to note all the outcomes previously described. Questionnaire 4 is a refusal questionnaire where all reasons of refusal or interruption of the VRH can be assessed standardized.

The investigators earned the Oncomfort Academy certificate and a Good Clinical Practice certificate. Midwives on the ward have already a year of experience with the VRH therapy for labor pain.

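### Parity is not planned to be recorded, balanced or adjusted for, although women of any parity are eligible; in a 38-woman trial, prespecifying it is a cheap improvement

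*Combined protocol and SAP*

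**What the plan says.** Section 11.2 describes an Excel list with variable block sizes: "The patients will be randomly allocated in either the either the control group or the VRH group in a 1:1 allocation". Neither that section nor sections 6 and 10 name a stratification factor. The criteria in sections 7.1 and 7.2 do not mention earlier births, so first-time and later mothers may both enter.

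The schedule in section 9 has no row for parity, obstetric history or demographics. Section 14.1 describes the first form in one sentence: "Questionnaire 1 is the registration checklist where inclusion and exclusion criteria are checked, the study number and randomization group is noted". The data collection form (Questionnaire 3) is described there as holding the outcomes, and parity is not an outcome in section 5.

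Section 11.4 begins with an unspecified descriptive analysis. It then names paired and unpaired t-tests, Mann-Whitney, chi-squared and Fisher's exact tests. No covariate appears.

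**The concern.** Blocking keeps the arm totals close to equal. It does nothing to balance a characteristic that is not a stratum. In a trial of 38 women, a visible chance difference in parity is quite possible. Parity is a plausible influence on labor pain, and also on progression of labor and need for epidural, both of which are listed secondary outcomes.

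Pain is self-reported and section 11.3 says the investigators are not blinded, so comparability of the arms is among the first things a reader will ask about. As written, the plan commits to no baseline table by parity and to no adjusted analysis. If an imbalance were noticed after the results are known, any correction would be post hoc and less credible.

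**Working it through.** **1. The plan's own sample size.** Section 11.1 sets the effect as follows: "we may expect a difference of the pain NRS means of 2 or more between the two arms". Its other inputs are an SD of 2 points per arm, 80% power and a two-sided 5% level. For a two-sample t-test the noncentrality is 2 / (2 × √(2/n)). Exact power is 0.781 at n = 16 and 0.807 at n = 17 per arm, which reproduces "17 evaluable patients are needed in each group to reach statistical significance". Allowing for 10% dropout, 17 / 0.9 = 18.9, so 19 per arm and 38 in total. The plan's figures are sound on their inputs.

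**2. Chance of a parity imbalance.** The documents give no nulliparous share p, so 0.4 to 0.6 is assumed. Counts in the two arms are taken as independent Binomial(19, p).

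| Gap in nulliparous women | Points | p = 0.4 or 0.6 | p = 0.5 |
|---|---|---|---|
| 4 or more | 21+ | 0.246 | 0.256 |
| 5 or more | 26+ | 0.135 | 0.143 |
| 6 or more | 32+ | 0.067 | 0.073 |

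At p = 0.3 or 0.7 the first row falls to 0.214. With 17 evaluable per arm, the chance of a gap of 4 or more is 0.189-0.229 for p from 0.3 to 0.7. As a cross-check, fix the total number of nulliparous women among the 38 (hypergeometric). Odd totals of 15 or 19 give 0.184 and 0.194, because a gap of exactly 4 is then impossible. Even totals of 16 to 22 give 0.325-0.330. The two together agree with about one in four.

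**3. Effect on the primary estimate.** Let β be the parity effect on the NRS change (T3 minus T1), assumed to be 0.5 to 1.5 points. A 4-woman gap shifts the between-arm difference by β × 4/19:

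- β = 0.5: 0.11 points
- β = 1.0: 0.21 points
- β = 1.5: 0.32 points

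The standard error, taking the planned SD of 2 to apply to the change, is 2 × √(2/17) = 0.69. The shifts are therefore 0.15 to 0.46 of a standard error, against a planned effect of 2.

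**4. What adjustment does to power.** With p = 0.5, R² = β² × 0.25 / 4 and the residual SD is 2 × √(1 − R²). With 17 per arm and one degree of freedom charged:

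| β | R² | Parity balanced | Single list, imbalance averaged |
|---|---|---|---|
| 0.5 | 0.016 | 81.2% | 80.0% |
| 1.0 | 0.063 | 83.1% | 81.8% |
| 1.5 | 0.141 | 86.1% | 85.0% |

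Unadjusted power is 80.7%. The last column allows for the variance inflation when arm and parity are correlated by chance. At the smallest effect, adjustment under the single list costs slightly more than it gains.

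**The case against.** The case against has force on several points.

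- *Validity.* Unstratified randomisation with unadjusted tests is valid. Chance imbalance does not bias the estimator on average or raise the type I error, and the confidence interval already allows for it. This stands, and it rules out calling the gap a bias.
- *Availability.* A reader might infer that parity is on no form and that an imbalance could never be seen or corrected. The documents do not support that. The questionnaires are described, not reproduced, and section 11.3 refers to an electronic patient file from which parity could probably be retrieved. What is missing is a commitment made in advance.
- *The rationale.* A reader might take section 4.1 as the protocol's own admission that parity matters: "The ability to cope with this pain is influenced by experiences that took place before childbirth". The sentence that follows it concerns unresolved earlier trauma, and the section does not mention previous births. The prognostic role of parity is therefore an assumption here.
- *The outcome.* The primary endpoint is a within-woman change, and section 10 has VRH offered at a common threshold of pain, dilatation and contractions. An effect of parity on pain level need not carry over to the change. This is a fair reason to treat 0.5-1.5 points as illustrative only.
- *The threshold.* The one-in-four figure depends on counting 4 women as sizeable. At 6 or more the chance is about 7%.

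None of this supplies a reason not to record and report parity. It lowers the stakes.

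**Conclusion.** The point holds as a cheap improvement, not as a flaw that undermines the trial. Parity is neither a stratification factor, nor a named data item, nor a covariate, while eligibility is open to women of any parity. On an assumed 40-60% nulliparous share, a gap of at least 4 women between arms has about a 25% chance, and of at least 5 about 14%. On an assumed parity effect of 0.5-1.5 NRS points, a 4-woman gap shifts the primary estimate by less than half a standard error. Any gain in power from adjustment is modest and depends on the size of the parity effect. The stronger reason to act is interpretability: in a small, unblinded trial that also compares progression of labor and epidural use, a parity table and an analysis fixed in advance are worth more than the same analysis assembled afterwards.

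**What to change.** Record parity (nulliparous or parous) on Questionnaire 1 at T0, and add it to the schedule in section 9. In section 11.4, state that parity will be reported by arm. Prespecify it as a covariate in the between-arm analysis of the primary outcome and of progression of labor. For epidural, with so few women, report results by parity or use an exact stratified test; a regression model would risk sparse cells.

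If no woman has yet been randomised, two parity-stratified variable-block lists are an option. Block sizes are not given; if the largest were 4, the arms could differ by at most 2 women within each stratum. The price is that the arms may not end at exactly 19 and 19. Allocation would also become somewhat more predictable, since section 11.3 has an unblinded investigator performing the randomisation. If randomisation has begun, keep the single list, and record and adjust.

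The cost is one tick-box and one degree of freedom. If parity has little effect, power under the single list falls marginally, from 80.7% to about 80.0%.
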